Neonatal health and improving neonatal mortality has become one of the top priorities globally. In Rwanda, hospital care has advanced significantly with the development of national neonatal care guidelines and widespread provider training. As advances in technology and resuscitation become more commonly available, many preterm, low birth weight and other high-risk infants are surviving the early neonatal period. However, upon discharge from the neonatal units, this at-risk population has little support for their health, nutrition and development in the community. To address this emerging need, Partners In Health in collaboration with the Ministry of Health and UNICEF, has created a pediatric developmental clinic (PDC) to follow the high-risk infants after discharge from hospitals and health centers. Prior to implementation, a community-based descriptive study assessing the baseline medical, nutritional and developmental needs of low-birth weight and preterm infants who are the target population of the pediatric development clinic was conducted (Baseline Phase One). Subsequently, after 1-2 years of implementation an evaluation of clinical, nutritional and developmental outcomes of children followed in PDC will be conducted in comparison with the baseline study outcomes (Post-PDC Phase Two). Ongoing research on PDC implementation will focus on research on patient and provider experiences, overall clinic processes, cost-effectiveness, expansion of the PDC model, decentralization to health centers, and longer term outcomes of children enrolled in the PDC to further help refine the PDC model (Post-PDC Phase Three).

Table of Contents

1. Background	5
2. Aims of the study:	6
3. Methods.....	8
3.1. Study description	8
3.2. Study design.....	8
3.3. Study sites	9
3.4. Study population	9
3.5. Selection of study population	10
3.5.1. Inclusion criteria	10
3.5.2. Exclusion and Stop Criteria	11
3.5.3 Sampling	11
3.5.4. Randomization	12
3.5.5. Proposed Intervention	12
3.5.6. Recruitment Methods.....	13
3.5.7. Subjects enrollment	14
3.6. Study Procedures	15
3.6.1. Procedures at enrollment and data collection.....	15
3.6.2. Outcomes, exposures, and confounders to be measured	18
3.6.3. Data Management.....	22
3.6.4. Analysis Plan	23
4. Study Limitations.....	26
5. Ethical Considerations	27
5.1. Risks and discomforts.....	27
5.2. Potential benefits.....	27
5.4. Informed consent	28
5. Ethical approval	29
6. Logistics	29
6.1. Distribution of responsibilities.....	29

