3.3. Study sites

Pre-PDC Phase One:

Phase One data collection took place in the Rwinkwavu District Hospital catchment area: Nyamirama, Mukarange, Mwili, Murama, Rwinkwavu, Kabarondo, Ndego, Kabare, and Ruramira sectors.

Post-PDC Phase Two:

Phase Two data collection will take place in the PDC clinics in the Rwinkwavu District Hospital catchment area: Rwinkwavu, Kabarondo, Ndego, Cyarubare and Ruramira Health Centers. Additional data collection on patient outcomes will be collected during household interviews at the homes of PDC patients.

Expanding -PDC Phase Three:

Data collection will take place in all PDC clinics in the Rwinkwavu and Kirehe District Hospital catchment areas. Household data collection will be conducted in the communities of Kirehe District.

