3.4. Study population

Pre-PDC Phase One:

All infants discharged from the Rwinkwavu District Hospital neonatal unit during the designated time period fulfilling the inclusion criteria: children were included if they were discharged between October 2011-October 2013 (prior to PDC implementation).

Post-PDC Phase Two:

All children enrolled in the PDC are eligible. PDC serves children up to age five years with prematurity, low birth weight, birth asphyxia, other perinatal risks, and other developmental delays.

Expanding-PDC Phase Three:

All children and their caregivers enrolled in the PDC clinics in S. Kayonza and Kirehe Districts are eligible. PDC serves children up to age five years with prematurity, low birth weight, birth asphyxia, other perinatal risks such as post CNS infections_cerebral malaria and meningitis, and other developmental delays.

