Our data collection is based on the use of independent data collectors. Data collection officers will be identified from the Family Strengthening Intervention Study staff (through coordination with their study coordinator) and will be trained on the use of the Ages and Stages Questionnaire as well as weight, length and head circumference measurements. Training sessions will take place at Rwinkwavu Center for Training and Operational Research. After completion of training, the data collection officers will be given a list of potential study participants. The data officers

will then contact the family's community health worker prior to making home visits and approaching the family for study participation.

Post-PDC Phase Two: All children enrolled in the PDC are eligible and the study will use routinely collected data from patient charts and EMR. In addition, patients who have been seen in the PDC clinic for 12 or more months will be contacted to participate in a household interview to be conducted by trained, independent data collectors. Patients will be identified from PDC enrollment records, and information will be extracted from patient charts for follow-up in the community (this includes caregiver name, geographic location of the household, and any relevant contact information for the household such as a phone number). Data officers will then contact the family's community health worker prior to making home visits and approaching the family for study participation.

Expanding-PDC Phase Three:

All children enrolled in the hospital neonatal units or PDC, and their caregivers, are eligible. The study will use routinely collected data from patient registers, patient charts and EMR in addition to qualitative methods. In addition, a list of PDC-eligible children prior to the opening of PDC in Kirehe (i.e., before May 2016) will be identified for household data collection to establish baseline status of high-risk infants prior to PDC. PDC providers (nurses, doctors, social workers, other parahealth professionals, volunteers) will be eligible to participate if they have been working in the PDC for at least 3 months.

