The majority of phase three data comes from existing program records, both paper-based and electronic as well as pre-existing de-identified data (see Appendix B for new tools being used in the PDC; Appendix F contains all the tools previously approved by RNEC). Additional data will be collected through household data collection and qualitative methods (new tools contained in Appendix B).

The procedure is as follows for using routinely collected program data: Data will be collected from electronic medical records (EMR) and paper forms that are part of routine programmatic record keeping (See Appendices B and F for all PDC data collection forms). Demographic characteristics, anthropometric measurements, clinical, counseling assessments, nutritional and developmental outcomes information will be extracted from the PDC EMR dataset and patient files. After extraction from the original dataset, data will be transferred into STATA (Stata Corp, College station, Texas, USA) for data cleaning and further statistical analysis. Patient identifiers will be removed and unique identification numbers will be assigned to the working dataset to respect patient confidentiality.

For household data collection, the procedure is as follows: neonatal unit registers will be reviewed for patients who would have been eligible for the PDC prior to the opening of the PDC in May 2015. Eligible caregivers of patients who were discharged alive will be contacted in the community to ask if they are willing to participate in the study. If caregivers provide written informed consent, they will be interviewed by trained data collectors using Android tablets about the current health, nutritional, and developmental status of their child as well as questions on the family environment. Household data collection tools are contained in Appendix A.

For qualitative data collection with PDC providers and patient caregivers, they will be invited by study staff (not PDC providers) to participate in focus groups and/or individual interviews. Only those who provide written informed consent will participate and interviews and/or focus groups

will be conducted at Partners In Health offices or other private spaces away from the PDC clinics.

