- Proportion of children with moderate or severe acute malnutrition (weight/height Z score < 2 or weight/height z score < 3) at the last visit.
- Proportion of children with a completed and documented ASQ in the reference quarter failing one or more domains on the ASQ.
- Mean/median scores on the overall ASQ
- Mortality rate in both groups
- Percentage of patients lost to follow-up
- Opportunities for learning and stimulation in the home, measured by the Rwanda-adapted HOME Inventory and the Rwanda DHS Early Childhood Development Index
- Caregiver mental health, measured by the Hopkin's Symptom Checklist which has been validated in Rwanda and used in Rwanda to assess symptoms of depression and anxiety for over twenty years
- Caregiver-child interactions and discipline practices, using the Kinyarwanda version of the Observations of Mother-Child Interactions (OMCI) as well as the Rwanda DHS Child Discipline Module
- Socioeconomic status of the household, using wealth index from the Rwanda DHS
- Exposure to daily hardships and household stressors

Expanding-PDC Phase Three:

Aim 5: To evaluate the implementation of PDC during expansion, including patient characteristics, provider experiences, quality of care, cost-effectiveness, patient experiences, and patient outcomes. Findings from this aim will be used for continuous quality improvement of the PDC and informing scale-up.

Primary Outcome: The primary outcome is the proportion of study participants alive who are meeting developmental and growth milestones.

Secondary Outcomes:

- Cost-effectiveness of the PDC model
- Adherence to PDC care protocols by PDC providers
- Quality of care
- Enrollment rates, clinic retention, and barriers to care
- Patient and provider experiences
- Impact of training and mentorship in the PDC protocol
- Evaluation of improved exclusive breastfeeding prior to PDC referral
- Impact of PDC mHealth tool on protocol adherence and child growth
- Impact of PDC on child outcomes in Kirehe

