6.2. Timeline

Pre-PDC Phase One

Period (months)	Oct - Nov 2013	Dec '13- Jul '15	Nov - Dec 2015	Jan - Feb 2015	Mar - May 2015
Activities					
IMBRC/NHRC/MOH/Hospital approvals					
Data collection and entry					
Data analysis and interpretation of results					
Preparation of manuscript					
Paper submission for publication					

Post-PDC Phase Two

Period (months)	Jun - Jul 2015	Aug - Oct 2015	Nov- Dec 2015	Jan - Feb 2016	Mar - May 2016
Activities					
Protocol amendment					
Data extraction for the aim 3					
Data extraction for the aim 4					
Data analysis and interpretation of results					
Preparation of manuscript					
Paper submission for publication					

Expanding-PDC Phase Three:

Period (months)	October 2016	Nov- Dec 2016	Jan-Jun 2017	Jul-Dec 2017	2018 and on
Activities					
Protocol amendment					
First expansion of PDC to Kirehe Health Centers					
Routine data extraction for aim 5					
Household data collection for aim 5					
Data analysis and interpretation of results					
Preparation of manuscript(s)					

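### The Kirehe pre-PDC household baseline has two cut-off dates 12 months apart, and no stated step identifies children already enrolled in PDC at interview

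*Combined protocol and SAP*

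**What the plan says.** Phase Three plans a household survey of high-risk children to show their status before PDC reached Kirehe. Two sections set its calendar limit:

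- Section 3.5.6 (Recruitment Methods, Phase Three): "a list of PDC-eligible children prior to the opening of PDC in Kirehe (i.e., before May 2016) will be identified for household data collection".
- Section 3.6.1 (Procedures, Phase Three): neonatal registers are searched for children who would have been "eligible for the PDC prior to the opening of the PDC in May 2015".

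Section 3.3 fixes the place: "Household data collection will be conducted in the communities of Kirehe District". Section 3.6.2 lists, among nine secondary outcomes for Aim 5, "Impact of PDC on child outcomes in Kirehe". The Phase Three timeline in section 6.2 has rows for "First expansion of PDC to Kirehe Health Centers" and "Household data collection for aim 5", and its earliest column is October 2016. On who may join the clinic, section 3.4 says "PDC serves children up to age five years with prematurity, low birth weight, birth asphyxia, other perinatal risks".

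For Aim 4a, sections 2 and 3.6.4 treat the Phase One children as a group without PDC services. Section 3.4 defines them by discharge between October 2011 and October 2013, and section 3.2 dates the first clinic's launch to April 2014.

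**The concern.** Neither 3.5.6 nor 3.6.1 gives an earliest discharge date. Apart from the under-five age limit, the disputed month is therefore the only calendar boundary of the Kirehe sampling frame. Someone building the list from one section would get a different set of children from someone using the other.

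Choosing a date does not by itself make the group unexposed. Being eligible before opening is not the same as being outside the clinic when interviewed. A child who joined PDC between opening and interview no longer shows what happens without it. If such children are counted as baseline, the comparison behind the Kirehe impact outcome loses contrast.

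**Working it through.** **1. Is it the same baseline?** Section 3.5.6 names Kirehe and 3.6.1 does not. Section 3.3 puts Phase Three household collection in Kirehe District, and section 3.2 dates the original launch to April 2014, so May 2015 cannot refer to that launch. Both statements describe the Kirehe baseline.

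**2. Size of the conflict.** May 2016 − May 2015 = 12 months of children in or out of the frame.

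**3. Does anything settle it?** The only other dated Kirehe item is the timeline row on expansion to health centres. That concerns a later step at other facilities, and its shading is not readable in the text available. It does not give the opening date.

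**4. What each mistake would do.** If the clinic opened in May 2015 and the May 2016 limit is used, the list takes in up to 12 months of children discharged after opening, from neonatal units that refer to PDC. If it opened in May 2016 and the May 2015 limit is used, 12 months of valid children are lost and the youngest are a year older at any given interview date.

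**5. Exposure before interview under either date.** The timeline columns run from October 2016 onward.
- October 2016 − May 2016 = 5 months.
- October 2016 − May 2015 = 17 months.

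These are minimum gaps, assuming that household collection falls within the timeline shown. PDC takes children up to age five, with referral from the hospital, health centres and the community (section 3.5.5), so a listed child could enrol in that gap.

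**6. Is enrolment screened?** Section 3.6.1 states three conditions: eligibility, discharge alive and consent. The Phase Three exclusion in 3.5.2 removes only children who fail the inclusion criteria, and 3.5.1 counts PDC enrolment as a way to qualify. No stated step looks for prior enrolment in the baseline group.

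**7. Direction.** Let c be the share of the baseline already enrolled at interview, pN the delay rate in the others, and pE0 and pE1 the rates in the enrolled without and with PDC.
- Wanted baseline rate: (1 − c)·pN + c·pE0.
- Enrolled children kept: (1 − c)·pN + c·pE1.
- Enrolled children excluded: pN.

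If PDC helps, pE1 < pE0, so keeping them lowers the baseline rate and shrinks the contrast. If enrolment is unrelated to outcome (pE0 = pN), exclusion recovers the wanted rate. If worse-off children enrol (pE0 > pN), exclusion also gives too low a rate, so the two analyses need not bracket the truth. The documents do not give c.

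As illustration only, assume delay of 50% without and 30% with PDC, enrolment unrelated to outcome, and full benefit in those enrolled. The kept-in difference is (1 − c) × 20 points: 18 at c = 10%, 15 at c = 25%, 10 at c = 50%.

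**8. Aim 4a.** A child discharged in October 2013 soon after birth reaches 12 months, the lowest assessment age, about October 2014, which is 6 months after launch. A Phase One child who enrolled in April 2014 would meet the 12-month enrolment rule for the PDC arm (section 3.5.3) from April 2015. Section 5.2 foresees later PDC enrolment of Phase One children. Sections 3.5.1 to 3.5.3, 3.6.3 and 3.6.4 have no rule against a child counting in both arms. Exposure and overlap are thus possible; nothing shows that either occurred.

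**The case against.** The date conflict may be a drafting slip. The wording of 3.6.1 is counterfactual and shows that an unexposed group was intended. PDC enrolment is already held in registers, enrolment forms and the electronic record, and the Aim 5 household tools, which are not reproduced, may ask about it. Aim 5 is mainly descriptive and Kirehe impact is one of nine secondary outcomes. All of this limits the consequence, and the claim of no check must be confined to the protocol text. It does not remove the conflict: the date defines a sampling frame, and intent is not a verification step.

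A second objection concerns the remedy. Section 3.5.5 lets PDC admit children for developmental delay or severe malnutrition, so dropping enrolled children may remove the worst-off and make the baseline look healthier. This stands, and the fix carries that caution.

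On Aim 4a, a reader might infer from the calendar that a definite share of the Phase One comparator was already exposed. The documents do not support that. The summary states: "Prior to implementation, a community-based descriptive study assessing the baseline medical, nutritional and developmental needs" was done, and sections 2, 3.5.5 and 3.6.4 describe the comparators as outside PDC. The collection dates cannot be read from the timeline. The sample was a selected one, and the 12-36 month age range may itself have left out the latest discharges. A share of discharge months is not a share of children. A child in both arms would breach the independence assumed by the chi-square or Fisher's exact test, but with positively correlated results the test tends to be conservative. That makes overlap the lesser issue.

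**Conclusion.** The Kirehe part holds. One baseline has two cut-offs 12 months apart, unresolved elsewhere. Under either date the planned period begins at least 5 or 17 months after opening, with no stated step to identify enrolled children. The likely effect, if PDC helps, is a Kirehe comparison pulled toward no difference.

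This rests on section 3.3 linking the two statements and on collection falling within the timeline shown. A reader might go further and conclude that the Kirehe baseline is contaminated. The documents show only that it could be, and no size of bias is claimed. The Aim 4a part is secondary and a request for clarification. The point should be fixed, mainly because the frame is ambiguous and the correction is cheap.

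**What to change.** **Kirehe**
- Reconcile sections 3.5.6 and 3.6.1 to one opening date taken from programme records.
- For each baseline child, record whether and when the child enrolled in PDC, from the caregiver or from the PDC register or electronic record.
- Report the number enrolled before interview.
- Show results with and without those children, stating that exclusion may make the baseline look healthier because PDC also admits children for delay or severe malnutrition.

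Cost: one date, one data field and one extra analysis. Where interviews are already done, enrolment dates can be sought in the clinic records.

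**Aim 4a**
- State the Phase One collection dates relative to April 2014.
- Where identifiers still allow matching, report how many Phase One children were enrolled before assessment, how many also appear in the PDC arm, and how many could not be matched.
- Count each child in one arm only. A Phase One record made before enrolment stays a valid unexposed record.

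Cost: a retrospective match that may be incomplete. Phase One is finished, the comparison file is de-identified, the linking file is kept for data quality checks on the electronic record, and paper records are destroyed after two years (sections 3.6.3 and 5.3). Each overlapping child loses one record. Section 2 marks this comparison as under way, so if outcomes were compared before the one-arm rule was set, the report should say so.

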3.5.7. Subjects enrollment

Pre-PDC Phase One:

After consent obtained from the caregiver by the data collector, the study participant will be enrolled and data collection will begin. All patient data will be stored in a password-protected access database.

Post-PDC Phase Two:

All children enrolled in the PDC are eligible and the study will use routinely collected data. Informed consent will be obtained for all participants who enrolled in PDC at least 12 months prior to data collection that willing to participate in household data collection.

Expanding-PDC Phase Three:

All children enrolled in the neonatal unit or PDC, and their caregivers, are eligible and the study will use routinely collected data. When routinely collected data is being used, we will not conduct additional informed consent. For any additional data collection with caregivers using qualitative methods or household data collection, caregivers will provide written informed consent for themselves and their child. Any PDC provider who participates in the study will provide written informed consent.

3.6. Study Procedures

3.6.1. Procedures at enrollment and data collection.

Pre-PDC Phase One:

After consent is obtained, data will be collected using a data collection form and the ASQs from 12 to 36 months of age on an Android tablet. The ASQ is a validated screening tool for child development that has also been translated to Kinyarwanda and validated for local use. The Ages and Stages questionnaire went through a validation process with the publisher to adapt the screening tool to Rwanda. The questionnaire was first translated from English to Kinyarwanda. After translation the questionnaire was field-tested. The questionnaire was then adapted to Rwandan cultural context and underwent field-testing again. The ASQ went through a final adaptation to Rwandan culture and was translated to English. It was then back translated to Kinyarwanda and finally submitted to the publisher for approval. Questions will be in a simple yes/no format and growth parameters of weight, height, head circumference and MUAC will be measured. Questions will be asked about the medical complications and developmental milestones will be assessed using the ASQs per age group. Upon data collection completion, the growth parameters and medical comorbidities will first be entered into the database and then the ASQ will be scored by a study staff. The scoring of the ASQ will be based on the answers of the caregivers. A score will be given to each answer. The ASQ has three possible answers: yes, not yet, or sometimes. At the end of the questionnaire the total score will be tabulated for each of the

five subsections based on a standard scoring methodology. Depending on the score, the questionnaire will be counted as normal or abnormal (developmental delay present).

Developmental delay will be defined as any single domain score that falls within the limits of concern or delay according to the ASQ scoring table at the end of the questionnaire.

Post-PDC Phase Two:

The majority of phase two data comes from existing program records, both paper-based and electronic as well as pre-existing de-identified data. The procedure is as follows for using routinely collected program data: After RNEC and MOH approvals are obtained, data will be collected from electronic medical records (EMR) and paper forms that are part of routine programmatic record keeping (See Appendix F for complete list of PDC routine data collection forms approved; new routine forms are contained in Appendix B). Demographic characteristics, anthropometric measurements, clinical, nutritional and developmental outcomes information will be extracted from the PDC EMR dataset and patient files. After extraction from the original dataset, data will be transferred into STATA (Stata Corp, College station, Texas, USA) for data cleaning and further statistical analysis. Patient identifiers will be removed and unique identification numbers will be assigned to the working dataset to respect patient confidentiality. As Aim 3 is a secondary dataset analysis of de-identified patient records, no individual patient consent procedure will be needed.

Aim 4 will include household interviews with caregivers of children who enrolled in PDC at least 12 months prior to data collection (see study tools for household data collection in Appendix A). These patients will be identified using EMR records and will be asked if they are willing to be contacted by the study team by PDC staff. If a caregiver is willing to participate, he/she will be contacted by the study team and complete informed consent prior to data collection. Consenting participants will complete an interview about the child's development, nutrition, parenting, and the home environment (see Appendix A for household data collection tool). Child development will be measured using the Ages and Stages Questionnaire, as has been previously approved for use in this study protocol. Appendix A contains all 20 age-specific forms of the Ages and Stages Questionnaires, however each caregiver will be asked only the 30 age-specific questions that are appropriate for their child; all questions for children of different ages will be skipped. Data will be collected on Android tablets using the software platform

KoboCollect.

Expanding-PDC Phase Three:

The majority of phase three data comes from existing program records, both paper-based and electronic as well as pre-existing de-identified data (see Appendix B for new tools being used in the PDC; Appendix F contains all the tools previously approved by RNEC). Additional data will be collected through household data collection and qualitative methods (new tools contained in Appendix B).

The procedure is as follows for using routinely collected program data: Data will be collected from electronic medical records (EMR) and paper forms that are part of routine programmatic record keeping (See Appendices B and F for all PDC data collection forms). Demographic characteristics, anthropometric measurements, clinical, counseling assessments, nutritional and developmental outcomes information will be extracted from the PDC EMR dataset and patient files. After extraction from the original dataset, data will be transferred into STATA (Stata Corp, College station, Texas, USA) for data cleaning and further statistical analysis. Patient identifiers will be removed and unique identification numbers will be assigned to the working dataset to respect patient confidentiality.

For household data collection, the procedure is as follows: neonatal unit registers will be reviewed for patients who would have been eligible for the PDC prior to the opening of the PDC in May 2015. Eligible caregivers of patients who were discharged alive will be contacted in the community to ask if they are willing to participate in the study. If caregivers provide written informed consent, they will be interviewed by trained data collectors using Android tablets about the current health, nutritional, and developmental status of their child as well as questions on the family environment. Household data collection tools are contained in Appendix A.

For qualitative data collection with PDC providers and patient caregivers, they will be invited by study staff (not PDC providers) to participate in focus groups and/or individual interviews. Only those who provide written informed consent will participate and interviews and/or focus groups

will be conducted at Partners In Health offices or other private spaces away from the PDC clinics.

When evaluating cost data, we will also access routine financial reports from Partners In Health and the Ministry of Health to assess program costs such as supplies, equipment, staffing, patient costs, supervision costs, and other inputs required for the PDC program.

